Methods: A total of 120 veterans with PTSD who are motivated to quit smoking will attend an initial diagnostic and baseline assessment session. Those who are interested, eligible, and who provide consent will be randomly assigned to receive ST+BA or ST+HSE and will be contacted by their individual study therapist to schedule the first treatment session. Participants will be stratified into treatment groups based on: 1) major depressive disorder (MDD; present versus absent), and 2) PTSD symptom severity. All participants will receive eight, individual sessions of ST+BA or ST+HSE. All participants will receive 20 minutes of identical standard smoking cessation treatment in each of the eight sessions. Those in the ST+BA condition will receive an additional 30 minutes of behavioral activation therapy; those in the ST+HSE condition will receive an additional 30 minutes of health education and information about smoking. All participants will receive 12 weeks of the nicotine patch and either nicotine gum or lozenge. Smoking cessation outcomes will be assessed 1, 2, 3, 4, 12, 20, and 26 weeks after the quit date.

Significance: This research has important clinical and public health significance because smoking is especially common among veterans with PTSD and it is the leading preventable cause of disease and disability. Reducing smoking rates among veterans with PTSD would result in substantially lower smoking-related illness and death in this vulnerable group of smokers. It would also reduce tobacco related healthcare costs charged to the VA. Study methods and findings may potentially be extended to smoking cessation treatment for patients with mental health disorders other than PTSD.

Background and Significance

PTSD is associated with an unusually high smoking prevalence and low cessation rates

The health, economic, and human costs of tobacco use are profound. Cigarette smoking remains the single largest preventable contributor to premature morbidity and mortality in the United States^{20,21}. Approximately 443,000 Americans die prematurely each year from tobacco-

related cancer, cardiovascular, cerebrovascular, and respiratory diseases²². The economic costs of tobacco use are also substantial. In the US, the annual costs of medical expenses and lost productivity resulting from tobacco-related disease, disability, and death are estimated at more than \$193 billion²².

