A total of 120 veterans with PTSD who are motivated to quit smoking will attend an initial diagnostic and baseline assessment session. Those who are interested and eligible and who provide consent will be randomly assigned to receive ST+BA or ST+HSE and will be contacted by the study therapist to schedule the first treatment session. Randomization of participants into treatment will be stratified on: 1) major depressive disorder (MDD; present vs. absent), and 2) bupropion use. All participants will receive eight, individual sessions of ST+BA or ST+HSE. All will receive 20 minutes of identical standard smoking cessation treatment in each of the eight sessions. Those in the ST+BA condition will receive an additional 30 minutes of behavioral activation therapy; those in the ST+HSE condition will receive an additional 30 minutes of health education and information about smoking. All participants will receive 12 weeks of the nicotine patch and either nicotine gum or lozenge. Smoking cessation outcomes will be assessed 1, 2, 3, 4, 12, 20, and 26 weeks after the quit date.

Recruitment

The proposed research will be conducted at the Madison VAMC in collaboration with the UW-CTRI. Due to challenges associated with recruiting a specialized population, we have devised a recruitment plan using two major recruitment pipelines.

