One hundred and twenty participants will be enrolled. For inclusion in the study, participants must: 1) report smoking an average of 6 or more cigarettes daily for at least six months; 2) report a desire to quit smoking; 3) meet criteria for *current* PTSD; 4) speak and read English; 5) agree to participate in the study; and 6) be \geq 18 years old.

Participants will be excluded from the study based on the following: 1) meeting criteria for psychotic or bipolar disorder; 2) psychoactive substance abuse or dependence (excluding nicotine dependence) within the past 6 months; 3) inability to give informed, voluntary, written consent to participate; 4) current use of any pharmacotherapy for smoking cessation not

provided by the researchers during the quit attempt; 5) use of non-cigarette tobacco or nicotine products as a primary form of tobacco/nicotine use; 6) being currently suicidal or homicidal, as assessed by VA suicide/homicide template questions administered to all veterans; 7) being medically unable to use the nicotine patch or nicotine gum/lozenge; 8) psychotropic medication changes within 2 months of study initiation and during active treatment; 9) current engagement in evidence-based therapies for PTSD or depression; 10) pregnant or trying to become pregnant; or 11) incarceration.

In addition, we will inform participants that, for research purposes, we prefer that they remain on the same psychotropic medication regimen throughout the trial. However, if it is necessary for a participant to alter treatment for his/her welfare, we will ask the participant to notify us immediately. Such participants will remain in the trial, but primary study analyses will be conducted with such participants excluded.

Any concerns regarding nicotine patch, gum, or lozenge use will be reviewed by the study clinician, who may interview patients should further information be required. All women of childbearing potential will be required to agree to use an approved method of birth control to prevent pregnancy during the period of nicotine replacement therapy (NRT) use. Participants with suicidal or homicidal ideation at screening will be referred for VA psychiatric care, and they will be excluded from the study. Study candidates who express imminent intent for harm to self or others at any point in the study will be referred for VA emergency care.

Assessments

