Primary Care PTSD Screen (PC-PTSD). The PC-PTSD⁸⁸ is a validated, four-item measure of PTSD with yes-no response options used by the Department of Defense Post-Deployment Health Assessment Program to identify veterans with possible PTSD. Two yes answers have been shown to yield sensitivity of .96 and specificity of .78⁸⁹. Study candidates who yield one or more yes answers on the PC-PTSD at the phone screen will be further assessed by an in-person diagnostic interview.

Clinician Administered PTSD Scale (CAPS). The CAPS⁹⁰ will be used to determine PTSD diagnostic status and severity. It will be administered at baseline and at the end of treatment (V10; see Table 1). The CAPS is a widely used and validated clinician interview for the assessment of PTSD. PTSD diagnosis on the CAPS is based on meeting the symptom criteria as defined in the most recent version of the Diagnostic and Statistical Manual of Mental Disorders (DSM). The CAPS shows strong internal validity⁹⁰. In addition, time since trauma, number of traumatic exposures, type of trauma, and time since original PTSD diagnosis will be assessed to aid in identifying factors that may be associated with treatment outcomes.

Structured Clinical Interview for DSM Axis I Disorders (SCID-I). The SCID⁹¹ is a widely used structured interview that assesses psychiatric disorders. The SCID-I has been shown to have very good reliability and validity⁹². The SCID-I will be administered at baseline, and only the depression module of the SCID-I will administered at the end of treatment (V10). If depression is noted in the SCID and participants are not already receiving clinical care, they will be referred to a clinical care provider. Questions pertaining to illicit drug use will be asked, but not recorded to protect participant privacy.

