PTSD Symptoms. Posttraumatic Stress Disorder Checklist-Military Version (PCL)⁹⁸ is a 17-item self-report scale that assesses PTSD symptom severity. Items are rated on a 5-point Likert scale according to how much the symptom bothered the respondent over the past month. The psychometric properties of this measure are excellent⁹⁸. In addition, a structured clinical assessment of PTSD via the CAPS will occur at baseline and end-of-treatment (V10).

Depressed Mood. We will use the Personal Health Questionnaire Depression Scale (PHQ) to assess depression. The PHQ is a well-validated tool for the assessment of depressive symptoms. The PHQ will be administered during active treatment and follow-up assessments. The depression module of the SCID-I will also be administered at baseline and end of treatment (V10).

Behavioral Activation. The Behavioral Activation Scale¹⁰⁰ assesses the sensitivity of the Behavioral Activation System, an index of the strength of motivation to engage in reinforcing activities (including goal-directed activity). Although those in the ST+BA group will record the actual *frequency* of engagement in reinforcing activities, self-monitoring is an important component of the ST+BA and could introduce poor treatment fidelity if utilized in the ST+HSE group. Thus, we have chosen to measure sensitivity of the Behavioral Activation System, which theoretically is the primary factor affected by BA. Sensitivity of the Behavioral Activation System will be assessed during active treatment and follow-up sessions. The psychometric properties of the Behavioral Activation Scale are strong¹⁰⁰.

Withdrawal. We will monitor withdrawal severity at baseline, throughout treatment, and

follow-up using the Wisconsin Smoking Withdrawal Scale, a 28-item scale that assesses nicotine withdrawal. It will allow for the assessment of the frequency, duration, severity, and temporal variability in withdrawal symptoms.

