We believe the EMA assessment schedule will produce the data needed for the study although it is less intensive (only one assessment per day) than other EMA protocols. In contrast to most research involving EMA, we are not attempting to characterize the relationships among measures at particular points in time (e.g., examining affect before and after individual cigarettes), which would require a much more frequent assessment schedule. Instead, we are interested in whether BA exerts effects on behavior and ratings on a more tonic basis, consistent with BA's putative mechanisms of action, and are using EMA in order to obtain time-stamped measures.

Treatment Adherence Measures

Therapist Competence and Adherence to Treatment. All treatment sessions in both conditions will be audiotaped, and a random selection of 25% (about 2 tapes per participant) of the audiotapes will be rated shortly thereafter by Drs. [name] and [name] to assess therapist adherence to and competence with the treatment protocol. Audio tapes will be maintained in a locked area accessible only the study staff and will be stored at the VA indefinitely, per VA policy. Separate rating checklists developed for the ST+BA and ST+HSE protocols will be used. Kappa will be reported for rated variables.

Adherence to Nicotine Replacement Therapy and side effects. Adherence to the nicotine patch, gum, and lozenge will be queried at each visit following initiation of NRT (Visits 6–9) and during the 12-week post-quit follow up call. Participants will be asked to return unused patches and gum/lozenge, which will be counted at each visit before dispensing new medication. NRT side effects will also be assessed at each visit. Potential differences in NRT use between treatment groups will be examined and incorporated into statistical models if a meaningful relation with outcomes is detected.

[figure not shown]
Adherence to BA. Patient treatment adherence to the ST+BA condition will be assessed by study personnel during weekly counseling sessions.

Study Procedures

Timing of Events

The study involves three basic phases: 1) Study Consent and Baseline; 2) Therapy Sessions; and 3) Follow-up. Figure 4 illustrates the timing of study events, and the procedures associated with these phases are included in the text that follows.

Figure 4: Study Timeline

Study Consent and Baseline

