Randomization Process. After the in-person screening assessment is complete, the participant will be assigned into ST+BA or ST+HSE. The following variables will be blocked in this order: 1) severity of PTSD, 2) depression status (MDD versus no MDD), and 3) bupropion use. Separate randomization tables will also be developed for those presenting via the two different pipelines (VA vs. community [via DVA]). This will ensure that any characteristics that are related to such entities are counterbalanced across groups. Following randomization, study staff will contact the participant to schedule the first treatment session.

Treatment

All participants will attend eight study visits in which they will receive ST+BA or ST+HSE

(V2-V9). The quit day will occur on the same day as the fifth treatment visit (V6: see Figure 4). At the beginning of each visit (prior to the administration of therapy), participants will complete a series of self-report measures that may include assessments of: 1) positive and negative affect (PANAS), 2) PTSD symptom severity (PCL), 3) depressed mood (PHQ), 4) level of behavior activation (BAS), and 5) withdrawal symptoms. Some assessments will not be administered at every visit to reduce assessment burden (see Table 1 for specific assessment schedule). Smoking status (continuous and point prevalence) will be assessed at every in-person visit following the quit date. Sessions may be completed via telemental health (TMH) at a community based outpatient clinic (CBOC) that is closer to a Veteran’s home or via phone in rare cases in which a Veteran is unable to travel a session in person.

Follow-up

All participants will receive follow-up phone calls at Weeks 12 and 20 (PA1 and PA2). They will also attend an in-person post-treatment follow-up visit to receive structured clinical assessments of PTSD and depression (V10). Participants will also attend an in-person follow-up visit at 26-weeks post-quit for nicotine abstinence bioverification (V11). Follow-up assessments will include measures of smoking status, positive and negative mood, PTSD symptom severity, depressed mood, sensitivity of the Behavioral Activation System, and withdrawal (see Table 1 for schedule).

Treatment Conditions

Treatment Conditions Overview

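### Three sections list different randomisation factors, the PTSD-severity stratum is tied to no instrument or cut, and the GLMM does not say whether it includes the factors

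*Combined protocol and SAP*

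**What the plan says.** All references are to the combined protocol and SAP.

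- Project Summary, Methods: "Participants will be stratified into treatment groups based on: 1) major depressive disorder (MDD; present versus absent), and 2) PTSD symptom severity".
- Design Overview: "Randomization of participants into treatment will be stratified on: 1) major depressive disorder (MDD; present vs. absent), and 2) bupropion use".
- Randomization Process (under Study Consent and Baseline): "The following variables will be blocked in this order: 1) severity of PTSD, 2) depression status (MDD versus no MDD), and 3) bupropion use". It adds: "Separate randomization tables will also be developed for those presenting via the two different pipelines", meaning VA and community recruits.
- Severity measures: the CAPS "will be used to determine PTSD diagnostic status and severity" (Screening/Diagnostic Assessments), while the PCL is a "17-item self-report scale that assesses PTSD symptom severity" (Treatment Effect Measures). Table 1 schedules both at baseline. The text on the in-person screening visit (V1) gives the CAPS the role of establishing diagnosis and puts severity among the self-report questionnaires.
- Bupropion: exclusion 4 bars "current use of any pharmacotherapy for smoking cessation not" supplied by the study. Exclusion 8 concerns changes in psychotropic medication, and the same section asks participants to keep a stable psychotropic regimen.
- Analysis: the GLMM is mentioned only under Power considerations, as inputs to a power macro. The one covariate rule is in the paragraph on nicotine replacement adherence: "Potential differences in NRT use between treatment groups will be examined and incorporated into statistical models if a meaningful relation with outcomes is detected".

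**The concern.** The Project Summary and the Design Overview each give a closed, numbered list of two factors, and each omits the other's second factor, so neither is a shortened form of the other. All three sections are current text. A reader cannot tell with certainty which factors were balanced by design. Even if the dedicated section governs, its first factor has no stated instrument, cut or number of levels.

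The analysis is silent on the same factors. Stratified randomisation removes chance variation in the factors between arms. A model that ignores prognostic factors still counts that variation in its standard error, so its test rejects too rarely under the null. What is at stake is a somewhat conservative primary test and a covariate choice left open, not the validity of the comparison.

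**Working it through.** **1. The lists side by side**

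| Section | MDD | PTSD severity | Bupropion use | Pipeline |
|---|---|---|---|---|
| Project Summary | yes | yes | no | no |
| Design Overview | yes | no | yes | no |
| Randomization Process | yes | yes | yes | separate tables |

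**2. The plan's own figure.** The stated power is 0.85 (45 per group, five time points, 25% dropout, 5% v 20%, random-effects variance 1, correlation 0.6, two-tailed; alpha is not stated, 0.05 assumed). The macro is not in the documents, so the figure can only be bracketed. A single time point gives 0.58. Compound symmetry, dividing n by (1 + 4 × 0.6)/5 = 0.68, gives 0.75. A random intercept with variance 1 alone gives 0.95. The 0.85 is neither confirmed nor shown wrong, and this point does not rest on it. No covariates or strata are among the inputs.

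**3. Number of strata at N = 120, all factors binary.** Each two-factor list gives 2 × 2 = 4 cells, 30 people per cell. The Randomization Process list gives 2³ = 8 cells (15 per cell), or 2⁴ = 16 if crossed with pipeline (120/16 = 7.5 per cell). Full crossing is an assumption. The expected number of cells with fewer than 4 people is the sum over cells of P(Binomial(120, p) ≤ 3). With MDD and severity split 50/50, 15% on bupropion and 25% community recruits, it is 6.6 of 16. Over bupropion 5–30% and community 10–50%, it runs from 2.7 to 10.5.

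**4. What the choice of list does to severity balance.** Simulation: permuted blocks of 4 within strata, the prevalences above, 8,000 trials per scheme. A between-arm gap in severity prevalence of 10 percentage points or more occurs in 29% of trials under the Design Overview list, 0% under the Project Summary list and 0.1–0.2% under the Randomization Process list.

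**5. What such a gap is worth.** Take mean abstinence of 12.5% (the midpoint of 5% and 20%) over two equal severity levels, and solve for the two rates:

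- OR 0.6: 15.25% v 9.75%, so 0.10 × 5.50 = 0.55 points
- OR 0.4: 17.29% v 7.71%, so 0.10 × 9.58 = 0.96 points
- OR 0.25: 19.34% v 5.66%, so 0.10 × 13.68 = 1.37 points

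The planned difference is 15 points.

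**6. Type I error with and without the factors.** Simulation: random-intercept logistic model, N = 120, five time points, 12.5% in both arms, variance 1, 25% random monotone dropout, 16 cells with blocks of 4, likelihood-ratio test of treatment with time as categories, nominal 0.05, 2,500 null trials per setting (SE about 0.004). The stated 0.6 correlation was not modelled separately. The two covariates are severity and MDD.

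| OR of each of four factors | Unadjusted | Two covariates | Four covariates |
|---|---|---|---|
| 1 | 0.047 | 0.050 | 0.051 |
| 0.6 | 0.045 | 0.049 | 0.056 |
| 0.4 | 0.041 | 0.050 | 0.059 |
| 0.25 | 0.022 | 0.043 | 0.052 |

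**7. How many covariates the data can carry.** Expected abstainers at week 26, before attrition: 60 × 0.05 + 60 × 0.20 = 3 + 12 = 15. In a single week-26 logistic model (6,000 null trials per setting, SE about 0.003), type I error was 0.044–0.054 unadjusted, 0.053–0.058 with two covariates, 0.055–0.061 with four, and 0.043–0.050 with four and a Firth penalty.

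**The case against.** The strongest reply is that the Randomization Process section is the dedicated one and contains every factor in the other two lists, while the others are a summary and an overview. On that reading the conflict is editorial, severity is almost always balanced, and the 29% in step 4 never arises. Most of this stands. A reader might infer that no randomisation tables could be built from this protocol; the documents do not support that, because the dedicated section can be followed once severity is defined. What remains is that no section says it governs, and it leaves severity undefined.

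A reader might also infer that exclusion 4 leaves nobody in the bupropion stratum. Its wording concerns drugs taken for smoking cessation, and exclusion 8 bars only psychotropic changes, so stable use for another indication is not clearly excluded. The text simply does not say whom the stratum covers. Nor do the documents settle the severity instrument: the measure descriptions allow the CAPS or the PCL, and the V1 text points towards self-report.

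On the analysis, it is fair to say that nothing obliges the trial to adjust, that the unadjusted test errs on the safe side, and that four covariates push type I error slightly above nominal in some settings. That argues for a short list fixed in advance, not for silence. Missing factors are also part of a wider gap, since no GLMM terms are stated at all; that the GLMM is the primary analysis is itself inferred from the Aim 1 power text.

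**Conclusion.** The plan contradicts itself on which factors govern randomisation, does not define the severity stratum, and does not say how the factors enter the GLMM. Confidence in these textual findings is high.

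The numerical consequence is small and conditional. Omitting prognostic factors makes the test somewhat conservative: slight at odds ratios of 0.6 or 0.4, and marked only if all four factors have an odds ratio of 0.25, which nothing in the documents supports. A 10-point severity gap would move the arm difference by at most about 1.4 of the planned 15 points, and such gaps are common only if the Design Overview list was the one used. Prevalences, odds ratios, block size, binary severity and full crossing are all assumed.

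A reader might infer a biased comparison or an inflated false-positive rate from the inconsistent strata or the small cells. Neither follows: allocation is random under every list, small cells only weaken within-cell balance, and the unadjusted test errs towards too few rejections. No gain in power from adjustment is claimed.

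**What to change.** 1. Make the Project Summary and Design Overview agree with the scheme actually used, apparently that of the Randomization Process section, including the pipeline tables.
2. Name the instrument that defines the severity stratum, its cut and its number of levels.
3. Reconcile the bupropion stratum with exclusions 4 and 8, so that a reader can see whom it covers. Which clinical rule applies is for the investigators.
4. State in the statistical section that the primary GLMM includes treatment, time and a short pre-specified set of the randomisation factors, for example MDD and the severity measure used to stratify. Report the unadjusted model as a sensitivity analysis.

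The cost is wording in three sections and one statistical sentence. Allocation does not change, and no new data are needed because the factors are required for randomisation. The downside is the event count: with about 15 abstainers expected at week 26, a long covariate list is unsafe, so the set must stay small or the model be penalised.
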